Fig 2 Comparison of Hormones on Meal Tolerance Test: Gastric Banding vs. Gastric Bypass

J Clin Invest. 2012 Dec 3;122(12):4667-74.

In this study we propose evaluating proof of concept that rapid delivery of nutrients directly to the jejunum promotes weight loss and glucose control that is superior to that seen when a non-nutrient liquid is delivered to the jejunum.

Proof of concept would justify the development of methods to allow direct delivery of bolus nutrient to

the jejunum that could be an alternative, lower cost, reversible alternative to GB surgery.

Preliminary Data

In late 2012 we initiated pioneering human proof-of-concept studies of our hypothesis that delivery of nutrients directly to the jejunum with standard NJT simulates the actions of GB. To our knowledge we are the first investigators to use the newly approved CORTRAK 2 Enteral Access System (EAS™) to rapidly and safely place jejunal tubes using

electromagnetic guidance in non-sedated outpatient volunteers. Key preliminary findings support both our technical approach and hypothesis.

So far we have:

- Successfully placed 23 of 25 nasojejunal tubes attempted in an average time of about 15 minutes (one tube could not be passed through the nasopharynx, 1 through the pylorus).
- Conducted 23 paired 3 hour 11 sample meal tolerance tests in obese adult subjects with type 2 diabetes. Each subject underwent a nasojejunal (NJ) and a paired oral (PO) test. Some data is shown in Figure 4.

We identified a significant increase in GLP-1, C-peptide, insulin and PYY and a trend towards a lower glucose in 7 paired tests with a dose of 120mls Ensure Nutrition Shake over 15mins (8kcal/min) and a much greater response in 3 individuals who underwent paired tests of 237mls Ensure Nutrition Shake over 30mins (also 8kcal/min). A single individual who underwent a paired test of 237mls over 15minutes (16kcal/min) had the greatest GLP-1 response but this dose was poorly tolerated and not repeated. All tubes were placed just distal to the ligament of Treitz at the entrance to the jejunum. (Unpublished: pending completion of assays).

Similar Work by Others

[figure not shown]

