2.0 OBJECTIVES AND PURPOSE

Specific Aims: In obese, ambulatory, adult patients with type 2 diabetes receiving mixed meal (intervention) or electrolyte solution (control) boluses daily via jejunal tube for 14 days, with 14 days follow up and with other oral nutrition permitted throughout, to compare the following:

Primary aim: weight change immediately following the intervention period between the study groups

Secondary aims: to compare the following within and between groups:

- From Day 0 to Day 14: caloric intake (as determined by consumption of provided food)
- From Day 0 to Day 14: weight change (within group)
- From Day 0 to Day 28: weight change
- From Day 0 to Day 14 and also from Day 0 to Day 28: waist and hip measurement, hormones and biochemical measures, physical activity, body composition, select symptoms, medication use, average self-monitored blood glucose level

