3.0 STUDY DESIGN

Study Design: Prospective, randomized, 2 group, pilot study: 14 days with jejunal tube, 14 days follow up. Subjects will receive intermittent bolus feeding into the jejunum with either mixed meal or non-nutrient liquid. The study will otherwise be the same. In this study the jejunal tube will be secured intraorally on an orthodontic molar band to avoid uncomfortable and conspicuous nasopharyngeal placement.

Recruitment Information sessions and study materials will be provided to clinic physicians who may refer subjects from within the LA County Healthcare Network to explain the study protocol. IRB approved flyers will be placed in approved recruitment areas. In addition clinic providers will request permission from patients to forward their names and contact information to the study recruiter if they meet eligibility criteria. If the patient agrees to have their name forwarded to the study team then this will be documented in the permanent medical record. The study recruiter will contact potential subjects and describe details of the study using an IRB script. If the potential subject remains interested in participating the PI and CoI will follow-up with further discussion and review of the protocol with the potential subject. Participants will be provided with diabetic education describing the signs and symptoms of hyperglycemia and hypoglycemia and their management. This will be provided by the study doctor when the protocol is discussed with the potential subject and will be reviewed at each subsequent visit.

Approved illustrations of the proposed intervention as well as the informed consent will be provided to the potential subject and they will be allowed to review this in their own time. All questions will be addressed by the PI and CoI before consent is signed.

Study Site: Edward R. Roybal Comprehensive Health Center.

Method:

Approximately Day -14: After Informed consent has been taken and dentition has been assessed, the study orthodontist will place dental spacers (small rubber strips) around an upper molar.

Approximately Day -7: Approximately 1 week (minimum 2 days) later a stainless steel orthodontic molar band modified to anchor the jejunal tube will be cemented to the selected molar. This will also be done in the Dental Clinic at Edward R. Roybal CHC without sedation or anesthesia. Two visits may be required for this step: 1 to measure for the dental band and the second to place it.

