Subjects will have a 10 French 140cm tube placed using a CORPAK EAS™ by the PI or CoI following standard technique and will be randomized to the intervention or control group. (See Appendix A: Tube Placement Using EAS™). It usually takes about 20 minutes to place the tube but can take as little as 5 minutes or up to an hour. If the tube cannot be positioned in the intestine within 1 hour it may be allowed to move into position naturally overnight. In this case the participant would come back a day or 2 later to check that the tube has reached the correct position. In this case the tube feeds would only start when the tube is shown to be in the correct position.

Subjects will be provided with detailed instructions and logs for the following: (See Appendix B: Subject Packet).

1. Bolus nutrient administration and flushing of tube
2. Eating: to eat ad lib from provided meals of known caloric amount
3. Daily self-monitoring and tube care
4. 24 hour contact information
5. Need to monitor blood glucose prior to tube bolus
6. Use of FitBit activity monitor and daily activity

Prior to leaving, the subject will self-administer the first tube bolus and demonstrate by verbal response understanding of requirements for the study.

- Day 0-Day 14: (see Table 3)
- Intervention subjects will take mixed meal via jejunal tube at 10mls/min to satiety or to a maximum volume of 200mls 4 times a day. They will also take 200mls electrolyte solution 4 times daily orally.
- Control subjects will take electrolyte solution via jejunal tube at 10mls/min to satiety or to a maximum volume of 200mls 4 times a day. They will also take 200mls mixed meal solution 4 times daily orally.
- If for any reason the tube feed cannot be administered the remainder should be taken orally to ensure recommended daily intake of major nutrients and fluid is achieved.
- In addition all subjects will take the following daily: 2 10meq potassium chloride tablets, 2 600mg calcium tablets and 1 multivitamin tablet daily and 1/2tsp salt.
- In addition all subjects will be requested to eat ad lib from provided meals of known caloric amount.
- All subjects may also eat ad lib from very low or calorie “free” foods and drinks throughout the study from a provided list.
- Subjects will maintain a log of all food intake will check their daily temperature, tube position and symptoms and will contact the study team for specified symptoms or if they have any concerns they would like addressed.

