- As subjects adhering to very low-calorie diets usually have a fall in blood pressure, especially during the first week antihypertensive drugs will be discontinued unless moderate to severe hypertension is present.[33]

- Subjects will be requested to be as physically active as they like. Thus they are at liberty to increase, decrease or maintain their usual activity level.
- Similarly as most diabetic patients eating very low-calorie diets have marked improvement in hyperglycemia with blood glucose concentrations falling within the first one to two weeks oral hypoglycemic drugs will be discontinued for the first week of therapy. [33] An increase in activity level may also cause a fall in blood glucose levels. To aid in maintaining safe blood glucose levels subjects will be required to report to the study team if their blood glucose is over 250mg/dl on more than 2 consecutive measures or any value over 300mg/dl or less than 70mg/dl on any occasion. Symptoms of hypoglycemia (sweating, weakness, palpitations, confusion) will be reviewed with the participant at each visit. They will be advised to check their blood glucose if possible if such symptoms occur and to take one 15g glucose tablet (to be carried at all times) and repeat this every 15minutes until self-monitored blood glucose is over 80mg/dL or symptoms resolve.

Table 3 Summary of Nutrient Administration Days 0-Day 14

Item:	Intervention Group:	Control Group:
Ensure High Protein Shake (400kcal/800mls/100% protein RDA/day)	Via tube*	By mouth
Unflavored Pedialyte Electrolyte Solution (80kcal/800mls/~50% electrolytes/day)	By mouth**	Via tube*
Additional vitamins and electrolytes	By mouth	By mouth
Ad Lib food from that provided	By mouth	By mouth
Ad Lib “calorie-free” foods from provided list	By mouth	By mouth

*If unable to administer by tube the remainder to be taken by mouth

**Optional artificial flavoring (provided) may be added by subject if they wish to the orally ingested Pedialyte to increase palatability. This will be documented in the daily log.

Day 7: Subjects will return to the clinic for review of log and caloric intake. Medications will be triturated at the study clinician’s discretion in an attempt to attain euglycemia. The position of the tube tip will be assessed per FDA approved procedure by reinsertion of the subject’s own transmitting stylet and the tube will be repositioned if not located beyond the Ligament of Treitz.

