4.0 DRUG/DEVICE INFORMATION

4.1 DRUGS

The only drug to be used is optional generic acetaminophen in recommended dose.

- 4.1.1 Standardized amounts of non-prescription nutrients and electrolyte solution will be administered both orally and via NJ tube.
 - 4.1.1.1 High Protein Shake ® Abbott Park, Illinois, U.S.A. All subjects will take 800mls divided equally and administered 4 times a day. This will provide the following each day: 100% of RDA high quality protein, 400kcal, 800mls water, 20% of potassium requirements and 16% of sodium requirements (Per 14 fl oz. bottle: 210 calories, protein 25g, carbohydrate 23g, fat 2.5g, sodium 240mg, potassium 290mg)
 - 4.1.1.2 Unflavored Pedialyte ® Abbott Park, Illinois, U.S.A. All subjects will take 800mls of Pedialyte /day divided equally and administered 4 times a day. This will provide the following each day: 80kcal, 800mls water, approx. 40% of potassium requirements and 40% of sodium requirements. (Osmolality, mOsm/kg H₂O: 250; per liter: Sodium, mEq: 45; Potassium, mEq: 20; Chloride, mEq: 35; Zinc, mg: 7.8; Dextrose, g: 25; Calories: 100). No artificial sweeteners or flavors.
 - 4.1.1.3 The only difference is that the intervention group will receive the High Protein Shake via the tube and take the Pedialyte orally whereas the control group will take the Pedialyte via tube and the High Protein Shake by mouth.
 - 4.1.1.4 Klor-Con 1 tablets 10meq/tab. All subjects will take 2 tablets/day which will provide remaining potassium requirements (approximately 30-50% of RDA).
 - 4.1.1.5 Table salt (generic): All subjects will take 3grams/day (half a teaspoon) to provide remaining sodium requirements (approximately 30-50% of RDA).
- 4.1.2 Kirkland Signature Daily Multi Vitamins & Minerals 1/day will provide 50-100% of RDA
- 4.1.3 Kirkland Signature Calcium 600 Mg + D3 500 Tablets 2/day will provide 80-100% of RDA
- 4.1.4 Liquid acetaminophen (generic) 500mg/15mls: if desired for throat pain. Maximum 60mls/day.
- 4.2 Glucose tablets (generic) 15g: to be carried at all times for use in the event of hypoglycemia.

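### The stated contrast is jejunal meal versus jejunal non-nutrient liquid, but the assigned arms compare jejunal with oral delivery of the same 400 kcal/day meal

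*Combined protocol and SAP*

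**What the plan says.** The general descriptions name only the tube contents.

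- Section 1.0, in the proof-of-concept statement, expects weight loss and glucose control "superior to that seen when a non-nutrient liquid is delivered to the jejunum".
- Section 2.0, and the study summary in the same terms, describes patients "receiving mixed meal (intervention) or electrolyte solution (control) boluses daily via jejunal tube for 14 days".
- Section 3.0 opens with "Subjects will receive intermittent bolus feeding into the jejunum with either mixed meal or non-nutrient liquid. The study will otherwise be the same".
- Section 14.0 says randomization is to jejunal feeding with or without calories.

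Sections 6.0 and 13.0 use different language: the first randomizes the site of tube placement, and the second sets a relevant difference of 30% between sites.

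The regimen itself is set out elsewhere. Of controls, the Day 0 to Day 14 instructions in Section 3.0 say "They will also take 200mls mixed meal solution 4 times daily orally". Table 3 shows the same exchange, and Section 4.1.1.3 presents it as the sole difference between arms: "the control group will take the Pedialyte via tube and the High Protein Shake by mouth". Intervention patients take the electrolyte by mouth. Tube volume is limited by satiety ("Intervention subjects will take mixed meal via jejunal tube at 10mls/min to satiety or to a maximum volume of 200mls 4 times a day"), while the oral volume is a fixed 200 mL four times a day.

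**The concern.** A reader of the aims would expect the arms to differ only in what enters the jejunum. In fact they also differ in what is drunk: controls must swallow the full daily meal, and intervention patients swallow electrolyte instead. The aims allow other oral nutrition, but that does not describe a required meal given by mouth to one arm only.

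At stake is what the primary result may be called. If the weight difference is reported as jejunal nutrient against a non-nutrient infusion, it names a comparison that was not randomized. A null result could then be taken to mean that jejunal nutrient does nothing. Section 13.0 also sends the effect sizes to the design of later studies, which need to know which contrast they describe.

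The caloric-intake endpoint is exposed too. It is defined by consumption of provided food, without saying whether the assigned liquids count.

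**Working it through.** **1. Energy of the assigned liquids.** Table 3 gives "Ensure High Protein Shake (400kcal/800mls/100% protein RDA/day". The label in Section 4.1.1.1 is "Per 14 fl oz. bottle: 210 calories, protein 25g".

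- Shake: 14 × 29.57 mL = 414 mL; 210 / 414 = 0.507 kcal/mL; × 800 mL = 406 kcal/day (stated 400).
- Electrolyte: 100 kcal/L × 0.8 L = 80 kcal/day (stated 80).
- Total: 400 + 80 = 480 kcal/day, the mandatory minimum in Table 4, which draws no distinction between arms.

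The protocol's figures are reproduced.

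**2. Assignment by arm and route, at full volume (kcal/day).**

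| Arm | Tube | Mouth | Total |
|---|---|---|---|
| Intervention | 400 (meal) | 80 (electrolyte) | 480 |
| Control | 80 (electrolyte) | 400 (meal) | 480 |

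The electrolyte contains 25 g/L dextrose, so the terms non-nutrient and non-caloric are not literally true of it either.

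**3. What the difference estimates.** Write Y(tube, mouth) for mean weight change, with M for meal and E for electrolyte.

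- Contrast in the general descriptions, with oral liquids equal: Y(M, E) − Y(E, E).
- Contrast randomized: Y(M, E) − Y(E, M).
- Identity: Y(M, E) − Y(E, M) = [Y(M, E) − Y(E, E)] − [Y(E, M) − Y(E, E)].

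The trial therefore estimates the effect of the meal by jejunum minus its effect by mouth. A null result means those two effects are about equal, not that the first is zero. No arm receives electrolyte by both routes, so the two effects cannot be separated.

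**4. Tube volume limited, oral volume fixed.** Let f be the fraction of tube volume taken, with the remainder not drunk.

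- Intervention: 400f + 80. Control: 400 + 80f. Gap: 320(1 − f).
- f = 1: 480 v 480, gap 0. f = 0.75: 380 v 460, gap 80. f = 0.5: 280 v 440, gap 160.

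Section 3.0 also says that tube feed which cannot be given is to be drunk. It does not say whether stopping at satiety counts. If the remainder is drunk, total energy is equal again, but a share (1 − f) of the intervention meal goes by mouth, so the route contrast weakens.

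**5. Caloric-intake endpoint if only oral intake is counted.**

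- Remainder not drunk: control 400, intervention 80, gap 320 kcal/day.
- Remainder drunk: control 400 + 80(1 − f), intervention 80 + 400(1 − f), gap 320f.

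The built-in gap is thus at most 320 kcal/day, before any difference in ad lib eating.

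**The case against.** The strongest reply is that nothing is hidden and nothing is badly designed. Section 4.1.1.3 states the exchange openly, and Section 3.0 and Table 3 repeat it, so staff would deliver the right arms. The sentence about the study otherwise being the same can be read as meaning the same liquids, supplements and food. The hypothesis names no non-nutrient comparator, the primary aim is simply weight change between the groups, and the superiority phrase is a background sentence. Both arms have a tube and the same nominal volumes and energy, which answers the protocol's own worry in Section 1.0 about tube and volume effects on eating.

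Most of this stands. It shows that the arms are sound and that this is a fault of description. It does not rescue the description: the kind reading of Section 3.0 leaves Sections 1.0 and 14.0 naming a comparator that is not given alone, and Sections 6.0 and 13.0 speak of sites although every tube is meant to lie in the jejunum.

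Two stronger readings are tempting and are not supported.

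- A reader might infer that the trial cannot support its hypothesis. A positive result would support it, relative to oral delivery of the same meal, and that fits the gastric-bypass rationale.
- A reader might convert the controls' 400 kcal/day into a bias in kilograms or a loss of power. That would compare the actual control with an arm nobody proposes, one without the oral meal. Such an arm would have 80 against 480 required kcal/day and would confound jejunal nutrient with total energy. The shift would also depend on how much ad lib food the shake displaces, which the documents do not give.

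**Conclusion.** The protocol gives inconsistent accounts of its contrast, and the one in its aims and background is not the one its regimen randomizes. The primary comparison estimates jejunal-bolus versus oral delivery of the same daily meal, with the electrolyte route reversed. It is a valid comparison, but it cannot be reported as jejunal nutrient against a non-nutrient control alone, and a null result would not show absence of a jejunal effect.

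No number in the weight analysis changes. The quantified consequence is the possible artefact of up to 320 kcal/day in caloric intake if only oral intake is counted. This rests on the stated energy values and on full fixed oral volumes being taken. The nominal match of 480 kcal/day holds only if the full tube volume is taken or the remainder is drunk.

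**What to change.** Keep the arms and correct the wording.

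- In the study summary and Sections 1.0, 2.0, 3.0, 6.0, 10.0, 13.0 and 14.0, state one contrast: the same daily mixed meal assigned by jejunal bolus (electrolyte by mouth) versus by mouth (electrolyte by jejunal bolus).
- Drop the terms non-nutrient and non-caloric for the control, and the wording about sites.
- In Section 3.0, replace the sentence that the study is otherwise the same with one saying that both arms are assigned the same two liquids with the routes exchanged. Note there that tube volume is satiety-limited while oral volume is fixed. The sponsor should reconcile the text on tube volume, oral volume and drinking the remainder.
- Limit the primary conclusion to jejunal versus oral delivery of that meal.
- For caloric intake, count the assigned liquids by both routes in both arms, using volumes actually taken, and report ad lib intake separately.

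The cost is small: no new visits, procedures or patients. The Appendix C log records whether the tube feed and required oral feed were taken, the minutes of infusion, and any tube feed taken by mouth in mL. It has no line for volume infused, so one may be needed. The real price is a narrower claim: the trial could no longer be presented as showing superiority over a non-nutrient jejunal infusion.

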Recent work published in 2013 by Breitman et al, [17] Salinari et al, [18] and Marathe et al [19, 20] offer support of our concept. In these studies obese and non-obese and diabetic and non-diabetic subjects demonstrated significant increase in incretin hormone responses with jejunal feeding in studies of 2 and 3 days duration. Of note, Marathe et al [20] demonstrated a rate dependent effect of incretin stimulation with a greater effect observed at 4kcal/min vs. 2kcal/min. Corroborating data is also provided by Kaushik et al[21] who described release of satiating hormones with jejunal feeding during treatment for pancreatitis. Similarly Welch et al[22] reported a reduction in total caloric intake in normal volunteers offered an oral meal during a low calorie jejunal infusion of lipid but not saline. We consider these preliminary findings to strongly justify further objective evaluation and refinement of our approach.

Tube and Non-Nutrient Liquid May Alter Oral Food Intake

Rolls and Roe[23] reported in a study of 54 lean and obese women that the volume of liquid food infused intragastrically affected subsequent energy intake in both lean and obese women. There was a mean decrease in energy intake of a subsequent meal of 13% after a 400-ml preload compared with an iso-energetic 200-ml preload (P=.013). For this reason a controlled study should include a tube and non-nutrient liquid administration.

How jejunal feeding in this study differs from that used for standard jejunal feeding

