14.0 REGISTRATION GUIDELINE

14.1 Specify phone number to register the patients: [name].

Subjects will be randomized to caloric or non-caloric jejunal feeding.

Forms and records needed for registration:

- 14.2.1 Informed Consent
- 14.2.2 Daily self-monitoring sheet
- 14.2.3 Visit work sheet

At the time of registration, two copies of a signed and dated patient Informed Consent form with Bill of Rights will be available (an original for patient's medical chart; one copy for the patient; and the other for the PI's file).

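### The control infusion is called non-nutrient and non-caloric but carries up to 20 g dextrose (80 kcal) a day into the jejunum, so superiority over a nutrient-free infusion cannot be claimed

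*Combined protocol and SAP*

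**What the plan says.** Four places describe the control infusion as free of nutrient or energy:

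- Section 3.0 (Study Design) describes the jejunal bolus as "either mixed meal or non-nutrient liquid".
- Section 14.0 (Registration Guideline): "Subjects will be randomized to caloric or non-caloric jejunal feeding".
- Section 1.0, just before Preliminary Data, says the weight and glucose effect to be shown is one "superior to that seen when a non-nutrient liquid is delivered to the jejunum".
- Section 1.0, on tube and liquid effects on food intake, justifies the control arm: "For this reason a controlled study should include a tube and non-nutrient liquid administration".

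The product description says otherwise. Section 4.1.1.2 gives the control fluid's content per litre as "Dextrose, g: 25; Calories: 100", and its amount as "All subjects will take 800mls of Pedialyte /day divided equally and administered 4 times a day". Table 3 lists 80 kcal per 800 mL and assigns this fluid to the tube in the control group. Section 3.0 (Day 0 to Day 14) has controls infuse it at 10 mL/min, to satiety or at most 200 mL, four times a day.

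The Specific Aims in Section 2.0 use a neutral term, comparing patients "receiving mixed meal (intervention) or electrolyte solution (control) boluses daily via jejunal tube for 14 days". The formal hypothesis names no comparator.

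**The concern.** The nutrient in the control tube belongs to the class of stimulus the trial is built to test. Section 1.0 (Similar Work by Others) relies on a rate-dependent incretin response, "with a greater effect observed at 4kcal/min vs. 2kcal/min", and the title of that source in the reference list concerns glucose entry into the small intestine in type 2 diabetes. On the protocol's own reasoning, jejunal dextrose cannot simply be presumed inert.

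Two things are at stake. The first is interpretation: the arms contrast a larger and a smaller jejunal energy load, not nutrient with none. The second is later use: Section 13.0 says effect sizes from this pilot will feed future power calculations. An estimate filed as mixed meal against a nutrient-free control would carry the wrong label into the next trial.

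**Working it through.** **Inputs**

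- Control fluid: 25 g dextrose and 100 kcal per litre; 800 mL/day in four equal doses (Section 4.1.1.2).
- Infusion: 10 mL/min, at most 200 mL per bolus, both arms (Section 3.0).
- Mixed meal: 400 kcal per 800 mL (Table 3). Label: 210 kcal, 25 g protein, 23 g carbohydrate and 2.5 g fat per 14 fl oz (Section 4.1.1.1). 14 × 29.57 mL = 414 mL.

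**1. Reproduce the plan's figure.** 100 kcal/L × 0.8 L = 80 kcal/day, as stated in Table 3 and Section 4.1.1.2.

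**2. Dextrose by control tube.** 25 g/L × 0.8 L = 20 g/day. Per bolus: 25 × 0.2 = 5 g and 100 × 0.2 = 20 kcal. At 4 kcal/g, 20 g gives 80 kcal, so dextrose accounts for all the stated energy.

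**3. Energy rate.** Control: 0.100 kcal/mL × 10 mL/min = 1.0 kcal/min. Intervention: 400/800 × 10 = 5.0 kcal/min. From the label: 210/414 = 0.507 kcal/mL, hence 5.07 kcal/min and 406 kcal/day.

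**4. Tube contrast at full volume** (label values × 800/414 for the mixed meal)

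| Per day by tube | Intervention | Control |
|---|---|---|
| Energy, kcal | 400 (406 from label) | 80 |
| Carbohydrate, g | 23 × 1.932 = 44.4 | 20 |
| Protein, g | 25 × 1.932 = 48.3 | none listed |
| Fat, g | 2.5 × 1.932 = 4.8 | none listed |

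The ratio is 400/80 = 5 for energy and 44.4/20 = 2.2 for carbohydrate.

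**5. Total prescribed energy.** Each arm takes both products, one by each route: 400 + 80 = 480 kcal/day, matching the minimum in Table 4. Total prescribed intake is therefore balanced. The discrepancy concerns only what reaches the jejunum.

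**6. Sensitivity, by assumption only.** The documents give no response at 1 kcal/min, and no SD, effect size, alpha or power for the 10 per group. Suppose 10 per group had 80% power (two-sided 5%, normal approximation) against a nutrient-free control. That needs a standardised difference of (1.960 + 0.842) × √(2/10) = 1.253. If a fraction r of that difference remains, power is Φ(2.802r − 1.960):

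| r | Power |
|---|---|
| 1.0 (dextrose inert at this rate) | 80% |
| 0.9 | 71% |
| 0.8 | 61% |
| 0.7 | 50% |
| 0.6 | 39% |

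The row r = 0.8 is what strict proportionality to energy rate would give, (5 − 1)/5. Nothing in the documents establishes that proportionality.

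**The case against.** The best defence is that this is loose wording around a disclosed and deliberate design. The composition appears in Table 3 and Section 4.1.1.2, and its energy is counted in the 480 kcal minimum. Section 4.1.1.3 explains the route swap. The Specific Aims say electrolyte solution, and Section 13.0 simply compares the two groups. An equal-volume bolus still controls for tube and volume, the stated reason for having a control. If dextrose has any of the hypothesised effect, the arm difference shrinks, so a positive result would be conservative.

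Most of this stands. It preserves the randomised comparison and shows that a positive finding would hold against the fluid actually used. It does not rescue the Section 1.0 conclusion, which names a non-nutrient liquid, or the descriptions in Sections 3.0 and 14.0, which the product data contradict.

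The defence is also right about size. Both cited rates, 2 and 4 kcal/min, exceed the control's 1 kcal/min, and they concern incretin response, not weight. Preliminary Data reports a much greater hormone response to 237 mL than to 120 mL at the same 8 kcal/min, so rate alone does not set the response. A reader might infer that the arm difference will be 20% too small, or that it must understate the effect. The documents support neither: the loss could be nil.

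**Conclusion.** The point holds in a limited form. By the protocol's own figures the control infusion is neither non-nutrient nor non-caloric: it delivers up to 20 g dextrose and 80 kcal/day to the jejunum, one fifth of the intervention arm's jejunal energy. These are ceilings, because boluses stop at satiety and any part not given by tube is to be taken by mouth.

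Two statements are therefore unavailable: superiority over a nutrient-free jejunal liquid, and, after a null result, absence of an effect of jejunal nutrient.

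A reader might go further and infer that the trial cannot support its conclusions at all. That does not follow. The Specific Aims comparison is answerable as written, a five-fold difference in prescribed jejunal energy remains, and only the mixed meal supplies protein and fat. The energy and dextrose figures rest on the documents and simple arithmetic. Any figure for attenuation or lost power is an assumption.

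**What to change.** 1. Reconcile Sections 1.0 (both places), 3.0 and 14.0 with Table 3 and Section 4.1.1.2 by describing the comparator as a low-calorie dextrose-electrolyte solution.
2. Restate the proof-of-concept conclusion, and in Section 13.0 the effect estimate meant for future power calculations, as jejunal mixed meal against that solution: up to about 400 versus 80 kcal/day by tube, with protein and fat only in the mixed meal and the other product taken by mouth in each arm.
3. Add to Section 13.0 that the difference may understate the effect against a nutrient-free control by an unknown amount, possibly nil. Give no attenuation figure unless it is labelled as an assumption.
4. Report delivered jejunal volume and energy by arm. The daily log (Appendix C) records whether each tube feed was given, the volume taken by mouth instead, and the infusion time. Tube volume can be derived as 200 mL minus the oral part, with time × 10 mL/min as a check where a bolus was stopped early and the remainder was not drunk.

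The cost is wording, one derived variable and a slightly less favourable claim. No visit, procedure or sample size changes. Whether to change the fluid is for the sponsor.
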